- **Randomization Plan:** We will use a 6-block randomization scheme to ensure that the rolling enrollment process across multiple food bank sites will distribute participants equally into each study arm over time. This scheme will be generated using the website www.randomization.com for each food bank site separately, which will create a list of the order of randomization by sequential participant ID.
- **Process Responsibilities:** UCSF will be in charge of creating the randomization scheme for each site. This will include generating the randomization list, preparing sealed envelopes by participant ID, and mailing them to each site to open as recruitment progresses. In the event a participant ID is not used (e.g., a client withdraws consent upon learning what group he/she is randomized to), site study staff should note the participant ID number, destroy the number and envelope, and report the event and ID number to UCSF. UCSF staff will determine if any adjustments need to be made to maintain balance between assignments to intervention and control groups, and will instruct study staff accordingly.

Participant Identification Numbers by Study Site	
Site	ID Numbers
Houston	101-399
Detroit	401-699
Oakland	701-999

- **Procedure for Randomizing a Participant:** The research assistant at each food bank will enroll participants into the study. No staff member will know the randomly selected allocation of the participant until the HbA1c screening, informed consent process, and baseline survey is completed. At the conclusion of this baseline visit, the staff member will open the sealed envelope that corresponds to the participant ID number of the enrolled client and determine the arm assignment, either immediate intervention or waitlist intervention.
- **Best Practices for Using Randomization Envelopes:** Study staff that participate in enrollment activities should use the following best practices to ensure consistency in the randomization process, and to foster a satisfactory client experience.
 - Have all of your enrollment materials available when you are meeting with a new participant (e.g., consent forms, education materials, survey materials, and randomization envelopes)
 - It is especially important to have the participant’s randomization envelope at your table (and in plain sight) during the entire enrollment process
 - Have only 1 randomization envelope at the table for each participant

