13.4.4 Statistical analyses

For all the outcomes specified above, we will determine significant improvements using an ANCOVA specification:

$$Y_{i,t=1} = \beta_0 + \beta_1 T_i + \pi Y_{i,t=0} + \varepsilon_i$$

Where $Y_{i,t=1}$ is the given outcome variable measured post-treatment, $Y_{i,t=0}$ is its baseline value, T_i is an indicator for being assigned to treatment, and ε is the error term. Since randomization is at the individual-level, HuberWhite standard errors will be used. β_1 will provide the intent-to-treat effect.

Loss to follow-up

We intend to collect follow-up data on at least 80% of participants. We will conduct a formal missingness investigation to determine if the attrition rate differed between intervention and waitlist groups. If treatment status is found not to significantly affect attrition at the 5 percent significance level, then all estimation will proceed without any adjustment for attrition. If attrition is found to be related to treatment status, we postulate that attrition will be higher for the control group, and will employ Lee bounds to obtain bounds on our treatment estimates which are robust to this attrition (<https://ideas.repec.org/c/boc/bocode/s457477.html>). Multiple imputation for missing outcome data will also be explored as sensitivity analyses (<http://aje.oxfordjournals.org/content/175/3/210.full>).

Per protocol/exposure to treatment

Among those with complete baseline and follow-up A1c ascertainment, we will also examine the influence of the amount of exposure to the program. Specifically, we will determine whether the

participants who met our criteria for being “engaged” in the program (overall and by specific intervention component) had larger effects than those who were less engaged.

In this analysis, because the randomization benefits will be lost, we will adjust for other covariates in our model that we hypothesize to influence A1c and self-management improvements: age, gender, race/ethnicity, educational attainment, language, and site/location.

Subgroup analyses

While we are randomizing within sites, we also plan to conduct subgroup sensitivity analyses by both adjusting for site and examining changes within site to determine differential effectiveness by location. Site-specific differences will be shared with the food banks, but only reported publicly in manuscripts if found to be significantly different.

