13.5.4 Statistical analyses

For each of the outcomes from the utilization analysis we would assess the impact of the intervention using the following specification:

$$Y_i = \beta_0 + \beta_{1,i}T + \beta_{2,i}Post + \beta_{3,i}T * Post + \epsilon_i$$

Where Y_i is the given outcome variable, T_i is an indicator for being assigned to treatment, $Post$ is an indicator that the observation is from the post intervention time period, and ϵ_i is the error term. The impact of the intervention is measured by β_3 which measures the intent to treat effect – or the change in the outcome of interest for the treatment group compared to the change in the outcome of interest for the wait-list group. Since randomization is at the individual-level, HuberWhite standard errors will be used.

Loss to follow-up

We intend to follow the same procedures for loss to follow-up as specified in the analysis of the primary study outcome (HbA1c). We will conduct a formal missingness investigation to determine if the attrition rate differed between intervention and waitlist groups. If treatment status is found not to significantly affect attrition at the 5 percent significance level, then all estimation will proceed without

any adjustment for attrition. If attrition is found to be related to treatment status, we postulate that attrition will be higher for the control group, and will employ Lee bounds to obtain bounds on our treatment estimates which are robust to this attrition. Multiple imputation for missing outcome data will also be explored as sensitivity analyses.

Subgroup analyses

While the study is randomizing within sites, we also plan to conduct subgroup sensitivity analyses by both adjusting for site and examining changes within site to determine differential effectiveness by location. Site-specific differences will be shared with the food pantries, but only reported publicly in manuscripts if found to be significantly different.

Other planned subgroup analyses (as specified in our hypotheses) are by baseline glycemic control (>9%) and food security status.

14 Quality Control Procedures

Data integrity and study credibility depend on factors such as:

- Ensuring adherence to the protocol
- Obtaining complete follow-up information on all participants enrolled
- Using quality control measures to establish and maintain high standards for data quality

Quality control procedures for point-of-care testing is described in **section 7**.

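### The primary ANCOVA leaves out site although allocation is blocked within site, so its standard error is somewhat too large if site is prognostic; the likely loss is small and the remedy nearly free

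*Combined protocol and SAP*

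**What the plan says.** Section 8, Randomization Plan, sets the block size ("We will use a 6-block randomization scheme") and makes site a stratification factor: "This scheme will be generated using the website www.randomization.com for each food bank site separately".

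Section 13.4.4 gives one ANCOVA for HbA1c and the secondary outcomes. In plain notation it is Y1 = b0 + b1·T + π·Y0 + e, where T is the assigned arm and Y0 the baseline value of the outcome. It has no site term. On variance it says: "Since randomization is at the individual-level, HuberWhite standard errors will be used".

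Site appears in two other places in 13.4.4. Under subgroup analyses: "While we are randomizing within sites, we also plan to conduct subgroup sensitivity analyses by both adjusting for site". In the exposure (per-protocol) model it is one of the "covariates in our model that we hypothesize to influence A1c and self-management improvements: age, gender, race/ethnicity, educational attainment, language, and site/location". The plan therefore treats site as possibly prognostic for HbA1c, but uses it only outside the primary analysis.

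**The concern.** When allocation is balanced within each site, differences between sites contribute almost nothing to the treatment contrast, so the true variance of b1 does not contain them. A model without site leaves those differences in the residual, and the reported variance still counts them. The Huber-White estimator allows for unequal residual variances. It does not know that the design balanced the arms within site, so it keeps the excess.

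At stake is how accurately the primary result states its own uncertainty. The confidence interval would be wider than the design justifies, the nominal 5% test would run below 5%, and some of the precision bought by stratifying would be given up. There is also a practical matter. Both models are planned, and if they fell on opposite sides of 0.05 the model labelled primary would decide the trial's conclusion.

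**Working it through.** **Inputs from section 13.4.1.** Two-sided alpha 0.05; power 90%; difference 0.4 (9.5 to 9.1); SDs 1.6 and 1.9; baseline to follow-up correlation 0.51; one baseline and one follow-up measurement; 300 per arm.

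**Input not in the documents.** R², the share of the baseline-adjusted residual variance that site explains. Assumed range: 0 to 10%.

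**Step 1: reproduce the plan's figure.** n per arm = (1.6² + 1.9²)(1 − 0.51²)(1.960 + 1.282)² / 0.4² = 299.8, rounded up to 300. The adjusted SDs (1.376 and 1.634) and the relative efficiency (1.352) also agree. The pooled adjusted SD is √[(1.6² + 1.9²)/2] × √(1 − 0.51²) = 1.511. The standard error at 300 per arm is 1.511 × √(2/300) = 0.1234.

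**Step 2: formulas under site-blocked allocation.** The true SD of b1 is 0.1234 × √(1 − R²), with or without site in the model. The model without site reports 0.1234; the model with site reports 0.1234 × √(1 − R²). Hence:

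- excess in the reported standard error without site: 1/√(1 − R²) − 1
- true size without site: 2Φ(−1.96/√(1 − R²))
- power without site: Φ(1.2816/√(1 − R²))
- power with site: Φ(3.2415/√(1 − R²) − 1.96), where 3.2415 = 1.960 + 1.2816

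| Assumed R² | SE too large by | SE with site | True size, no site | Power, no site | Power, with site | Gain (points) |
|---|---|---|---|---|---|---|
| 0 | 0 | 0.1234 | 5.0% | 90.0% | 90.0% | 0 |
| 1% | 0.5% | 0.1227 | 4.9% | 90.1% | 90.3% | 0.2 |
| 2% | 1.0% | 0.1221 | 4.8% | 90.2% | 90.6% | 0.3 |
| 5% | 2.6% | 0.1202 | 4.4% | 90.6% | 91.4% | 0.8 |
| 10% | 5.4% | 0.1170 | 3.9% | 91.2% | 92.7% | 1.6 |

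Gains are taken before rounding.

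**Step 3: simulation check.** Three equal sites, blocks of 6 within site, 600 analysed, Huber-White errors, 4,000 replicates per setting. At R² = 10% the estimator's SD was 0.118 with or without site, while the mean reported standard error was 0.1234 without site and 0.117 with it. At R² = 5% the SD was 0.122, and the mean standard errors were 0.1234 and 0.120. At R² = 0 the two standard errors were identical. A separate run of 6,000 replicates gave power of 91.3% without site and 92.7% with it at R² = 10%, and 90.4% and 91.5% at R² = 5%. With 4,000 replicates a rejection rate near 5% carries Monte Carlo error of √(0.05 × 0.95/4000) = 0.34 points, so the table uses the analytic sizes.

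**Step 4: what the R² values mean.** For three equal, evenly spaced sites, the gap between the extreme sites after baseline adjustment is 2 × √(1.5 × R²) × 1.511. That is 0.37, 0.52, 0.83 and 1.17 HbA1c points at R² of 1, 2, 5 and 10%.

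**Step 5: attrition.** The sizes in the table assume exact balance within site among those analysed. If 20% are lost at random, about one fifth of the imbalance returns. At R² = 10% the relative true variance becomes 1 − 0.8 × 0.10 = 0.92, and the size is 2Φ(−1.96/√0.92) = 4.1% instead of 3.9%.

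**The case against.** The strongest reply is that the plan already prespecifies a site-adjusted analysis, so readers will see that estimate; only the label of primary is in dispute. The error is also on the safe side: the estimate is unbiased and type I error is not inflated. The size of the loss is assumed, and R² of 5 or 10% needs gaps between extreme sites of two to three times the 0.4-point target effect. All of this stands, and it makes the point a minor one. It does not remove the mismatch between design and primary analysis, for which the documents offer no reason.

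Three stronger readings are tempting, and the documents do not support them.

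- A reader might infer that adding site lifts power from 90.0% to as much as 92.7%. But blocking has already reduced the true variance, so the model without site also runs above 90%. The gain is the difference between the two power columns, at most about 1.6 points over the assumed range.
- A reader might infer that the health care utilization model in section 13.5.4 has the same defect, because it also omits site. Its effect is the treatment-by-period interaction. With both periods observed, a constant site effect cancels from that contrast, and adding site indicators leaves the estimate unchanged (0.25427 both ways in a numerical check). Only the reported standard error moves, and none of the figures above carries over.
- A reader might infer bias or an invalid test. Neither follows; the direction is conservative.

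**Conclusion.** The point holds for the primary ANCOVA in section 13.4.4. Allocation is stratified by site, the primary model omits site, and the planned standard errors do not make up for it. Over an assumed R² of 0 to 10%, the reported standard error is 0 to 5.4% too large, the 5% test runs at 5.0% down to about 3.9% (slightly closer to 5% after attrition), and the power given up is 0 to about 1.6 points.

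These figures rest on the SDs, correlation and 300 per arm in section 13.4.1, on three equal sites for the gaps, and on an R² that the documents do not give. At R² = 0 nothing is lost. The plan's own covariate list makes some site effect plausible but says nothing about its size; at the more modest values of 1 to 2% the gain is 0.2 to 0.3 points. The main reason to change is that the primary analysis would then state its uncertainty in line with the way the trial randomizes. No figure is offered for the individual secondary outcomes.

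**What to change.** In section 13.4.4, make the primary model Y1 = b0 + b1·T + π·Y0 + s1·Site2 + s2·Site3 + e, where Site2 and Site3 are indicators for two of the three food banks, and keep the Huber-White errors. Use it for HbA1c and for the other outcomes analysed with that ANCOVA. Keep the model without site as the prespecified sensitivity analysis, and state which model decides the primary conclusion.

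The cost is two degrees of freedom and a short change of wording. No new data are needed: section 8 gives each site its own range of participant ID numbers, so site is known for everyone. This point calls for no change to section 13.5.4.

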1.1 Overview of the FAITH-DM Trial

The Feeding America Intervention Trial for Health—Diabetes Mellitus (FAITH-DM) is a randomized, controlled study of the implementation of a diabetes intervention in food pantry settings. Every effort has been made to enhance the feasibility of implementation while maintaining the rigor of a randomized, controlled trial. The intervention will be implemented in three food banks: Alameda County Community Food Bank (Oakland, CA), Gleaners Community Food Bank of Southeastern Michigan (Detroit, MI), and the Houston Food Bank, (Houston, TX). These food banks were chosen through a competitive application process after demonstrating their capacity to reach the population of interest (English- and Spanish-speaking adults with diabetes receiving food at food pantries) and carry out the study procedures according to the instructions laid out in this manual.

This research is critically important. In the pilot study recently completed, we observed significant improvements in self-management skills and competencies such as self-efficacy and medication adherence, and a trend toward improved glycemic control (HbA1c) and decreased risk of severe hypoglycemic events. Participants were highly satisfied with the diabetes-appropriate food distributed as part of the intervention. This work suggested that food pantries are a feasible site to engage vulnerable individuals in diabetes self-management efforts. We are excited to be able to determine the efficacy of this model.

Funding for FAITH-DM was provided by Feeding America and the Laura and John Arnold Foundation.

The study is listed on www.clinicaltrials.gov with identifier: NCT02569060.

FAITH-DM received approval from the Western Institutional Review Board (Protocol Number: FADiabetes2015, WIRB#: 2015169).

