Other planned subgroup analyses (as specified in our hypotheses) are by baseline glycemic control (>9%) and food security status.

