	11b	If relevant, description of the similarity of interventions	<hr/>
Statistical methods	12a	Statistical methods used to compare groups for primary and secondary outcomes	<hr/>
	12b	Methods for additional analyses, such as subgroup analyses and adjusted analyses	<hr/>
Results			
Participant flow (a diagram is strongly recommended)	13a	For each group, the numbers of participants who were randomly assigned, received intended treatment, and were analysed for the primary outcome	<hr/>
	13b	For each group, losses and exclusions after randomisation, together with reasons	<hr/>
Recruitment	14a	Dates defining the periods of recruitment and follow-up	<hr/>
	14b	Why the trial ended or was stopped	<hr/>
Baseline data	15	A table showing baseline demographic and clinical characteristics for each group	<hr/>
Numbers analysed	16	For each group, number of participants (denominator) included in each analysis and whether the analysis was by original assigned groups	<hr/>
Outcomes and estimation	17a	For each primary and secondary outcome, results for each group, and the estimated effect size and its precision (such as 95% confidence interval)	<hr/>
	17b	For binary outcomes, presentation of both absolute and relative effect sizes is recommended	<hr/>
Ancillary analyses	18	Results of any other analyses performed, including subgroup analyses and adjusted analyses, distinguishing pre-specified from exploratory	<hr/>
Harms	19	All important harms or unintended effects in each group (for specific guidance see CONSORT for harms)	<hr/>
Discussion			
Limitations	20	Trial limitations, addressing sources of potential bias, imprecision, and, if relevant, multiplicity of analyses	<hr/>
Generalisability	21	Generalisability (external validity, applicability) of the trial findings	<hr/>

Interpretation	22	Interpretation consistent with results, balancing benefits and harms, and considering other relevant evidence	_____
----------------	----	---	-------

Other information

Registration	23	Registration number and name of trial registry	_____
--------------	----	--	-------

Protocol	24	Where the full trial protocol can be accessed, if available	_____
----------	----	---	-------

Funding	25	Sources of funding and other support (such as supply of drugs), role of funders	_____
---------	----	---	-------

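### Sections 13.4.4 and 13.5.4 let a significance test decide whether planned site-specific results are published

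*Combined protocol and SAP*

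**What the plan says.** Section 1.1 states: "The intervention will be implemented in three food banks". Section 8 provides for a separate blocked list at each site ("We will use a 6-block randomization scheme").

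Under Subgroup analyses, section 13.4.4 plans to adjust for site and also commits to "examining changes within site to determine differential effectiveness by location". It then settles who sees the findings. "Site-specific differences will be shared with the food banks", but they are to be "only reported publicly in manuscripts if found to be significantly different". Section 13.5.4 repeats the rule for the utilization outcomes: "Site-specific differences will be shared with the food pantries, but only reported publicly in manuscripts if found to be significantly different".

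Nothing elsewhere in the manual withdraws or limits this. The remaining subgroups carry no such condition: "Other planned subgroup analyses (as specified in our hypotheses) are by baseline glycemic control (>9%) and food security status".

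Appendix H reproduces the CONSORT 2010 checklist. Item 18 lists what a report should contain: "Results of any other analyses performed, including subgroup analyses and adjusted analyses, distinguishing pre-specified from exploratory". It makes no exception for results that are not significant.

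**The concern.** A planned analysis should be reported whatever it shows. Here publication of the site results depends on their p-value, so the distortion comes from following the plan, not from departing from it. A filter of this kind does two things. It lets through estimates that are too large on average, because only large observed differences pass. It also holds back the estimates and intervals by which readers could judge whether the effect was similar in the three cities. Both effects are strongest when power is low, and a comparison between single sites has much less power than the overall comparison for which the trial was sized.

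The rule also leaves open what has to be significant. Neither section gives an interaction model, a significance level for site tests or a multiplicity rule. Neither says whether the comparison is of sites with each other or of one site's effect with zero.

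**Working it through.** **The plan's own figure.** Section 13.4.1 gives SDs of 1.6 and 1.9, a baseline to follow-up correlation of 0.51, a difference of 0.4, two-sided alpha 0.05 and 90% power by ANCOVA.

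- Adjusted SDs: 1.6 × √(1 − 0.51²) = 1.376 and 1.9 × √(1 − 0.51²) = 1.634, as printed in the plan.
- n per arm = (1.960 + 1.282)² × (1.376² + 1.634²) / 0.4² ≈ 300. The stated figure reproduces.

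**Precision at one site.** Assume three equal sites. The recruitment goal of 720 less 20% leaves 576, and 576 / 6 = 96 analyzed per arm per site.

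- SE of one site's effect = √((1.376² + 1.634²) / 96) = 0.218.
- 95% confidence interval for one site: ± 1.96 × 0.218 = ± 0.43 points.
- SE of the difference between two sites = 0.218 × √2 = 0.308.
- Smallest observed two-site difference significant at 5%: 1.96 × 0.308 = 0.60.
- Smallest observed difference, one site against the other two: 1.96 × 0.218 × √1.5 = 0.52.

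With the plan's projected 600 analyzed (100 per arm per site), the two-site threshold is 0.59, so the choice between 96 and 100 hardly matters.

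**What the filter lets through.** The documents give no expected difference between sites, so the true two-site difference *d* is an assumption, shown over a range. The observed difference is taken as normal with mean *d* and SE 0.308. It is published if its absolute value exceeds 0.604. The mean is of the absolute difference among those published.

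| True difference (assumed) | Chance of publication | Mean published difference | Ratio to truth |
|---|---|---|---|
| 0 | 5% | 0.72 | – |
| 0.2 | 10% | 0.75 | 3.7 |
| 0.4 | 25% | 0.79 | 2.0 |
| 0.6 | 49% | 0.85 | 1.4 |
| 0.8 | 74% | 0.94 | 1.17 |
| 1.0 | 90% | 1.06 | 1.06 |

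**Check with a joint test of the three sites.** A 2-df test of equal site effects, again with 96 per arm per site, gives the same picture. For assumed true effects of 0.2, 0.4 and 0.6 the power is about 20%. The spread between best and worst site then averages 0.87 among trials that pass, against a true spread of 0.4. With no true spread, 5% pass and their average spread is 0.83.

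**The other reading of the rule.** If the test is of one site's effect against zero, an effect equal to the 0.4 target would be significant at a given site in about 45% of trials.

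No magnitude is computed for utilization, because section 13.5 gives no variance for those outcomes. That half of the point rests on the wording alone.

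**The case against.** The rule is stated openly in advance, the food banks receive the site results, and site analyses are described as sensitivity work for which the trial is not powered. These points are true, but they do not answer the concern. Disclosure does not remove selection from the published record, and readers do not see what the food banks see. Low power is a reason to label the estimates exploratory and give their intervals, not to filter them by significance.

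Other objections limit the point, and they stand:

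- A reader might infer that the trial's results as a whole are reported selectively. The rule covers site-specific differences only. The primary intent-to-treat result, the overall secondary and utilization results, and the HbA1c >9% and food-security subgroups carry no such condition.
- A reader might infer that every site difference that reaches print must be exaggerated or false. Selection inflates the average, not each estimate, and at a true difference of 1.0 the average inflation is only about 6%.
- The near fourfold inflation belongs to one assumed value, 0.2. At 0.4 it is about twofold.
- The rule does not stop a manuscript from stating that no significant site difference was found, or from giving the site-adjusted overall estimate. What it withholds are the site estimates and their intervals.
- The Appendix H checklist is a blank form and does not override section 13. It shows an inconsistency within the manual, not a correction of the rule.

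**Conclusion.** The concern holds for the site-specific results in sections 13.4.4 and 13.5.4. Publication of a planned analysis is made to depend on its p-value, against item 18 of the checklist that the manual itself appends.

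For HbA1c, two sites must differ by about 0.60 observed points to be published, which is more than the 0.4-point effect the trial is built to detect. For true differences up to 0.4 the chance of publication is at most about 25%, and what is published averages 0.72 to 0.79. Moderate differences, and the estimates that would show consistency, would therefore usually go unpublished.

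These figures assume equal sites, 96 analyzed per arm per site, the plan's adjusted SDs, a two-sided 5% test between two sites, and an illustrative range of true differences. The primary inference is untouched, so this is a change the plan should make, not a flaw in its main conclusion.

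**What to change.** In both sections, replace the sentence on site-specific differences with:

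> Site-specific estimates with 95% confidence intervals and the treatment-by-site interaction test (site and treatment-by-site terms added to the stated model) will be reported in the manuscript or its supplement whatever their significance, labeled exploratory.

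In section 13.5.4 the treatment effect is the coefficient of treatment by period. The site interaction there should therefore be with that term, with the lower-order site terms included.

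The cost is one sentence in each section, a small amount of extra analysis, and a supplementary table for each outcome set (HbA1c with the survey outcomes, and utilization). Sample size, alpha, data collection and the primary analysis do not change.
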